4.3 Study Assessment

4.3.1 Schedule of Assessment

Table 2: Schedule of Assessments (All assessments except the ophthalmology exams and screening and enrollment visits may occur in person or via telehealth.)

	Screen Visit	Enrollment Visit (Baseline) (≤45 days)	M3 (+/-2 weeks)	M6 (+/-2 weeks)	M9 (+/-2 weeks)	M12 End of Study ¹ (+/-2 weeks)	Interim Visits ²
Inclusion/Exclusion Criteria	X	X					
Consent/Accent	X						
Demographic Information	X	X					
Enrollment	X ¹⁰	X					
Past Medical Hx (per CARRA registry)	X						
Physical Exam	X	X	X	X	X	X	X
Active Joint Count	X	X	X	X	X	X	X
Concomitant Meds (per CARRA registry)	X	X	X	X	X	X	X
Study Drug Adherence			X	X			
Dose/Instructions		X					
Drug Dispensation		X ¹²	X ¹²				
Ophthalmology Exam ³	X	See Ophthalmology Assessment Table 3 below The 1 st Dose of study drug cannot be administered until after the screening eye exam has confirmed no disease. The M12 End of Study eye exam can be done up to 4 weeks after the end of study visit.					
MyStudies App enrollment		X					
Physician Global		X	X	X	X	X	X
Parent Global		X	X	X	X	X	X
PROMIS® Measures ⁷	X	X	X	X	X	X	X
CHAQ		X		X		X	X
JAMAR		X	X	X			X
Duration of Morning Stiffness (Patient Reported)	X	X	X	X	X	X	X
JADAS		X	X	X	X	X	X
SAEs & ESIs (Per CARRA registry)	X	X	X	X	X	X	X
Quantiferon Gold/TB screen (drug can be administered in the absence of test results. Patient families will be instructed to not administer drug until a	X	X ¹¹					

	Screen Visit	Enrollment Visit (Baseline) (≤ 45 days)	M3 (+/-2 weeks)	M6 (+/-2 weeks)	M9 (+/-2 weeks)	M12 End of Study ¹ (+/-2 weeks)	Interim Visits ²
negative result is confirmed)							
Urine pregnancy screen ⁸		X ⁸	X ⁸	X ⁸	X ⁸	X ⁸	X ⁸
CBC	X ⁵		X ⁴	X ⁴			
HBsAg ⁹	X						
CMP	X ⁵		X ⁴	X ⁴			
ESR/CRP ⁴	X ⁴		X ⁴	X ⁴	X ⁴	X ⁴	
ANA	X ⁶						
HLA-B27, RF, anti-CCP (Per CARRA Registry)	X						
Covid-19 Survey ¹³	The patient/guardian will complete the Covid 19 Survey using the MyStudies App every week before study drug administration.						

¹ End of study visit should be conducted at the end of the follow up period or if the participant discontinues the study for any reason, including development of polyarticular JIA or anterior uveitis, escape from treatment arm, safety concern, or withdrawal of consent.

² Interim visits occur whenever a study participant is evaluated clinically outside of the regularly scheduled study visit schedule for symptoms concerning for active arthritis, new anterior uveitis, or SAEs.

³ Baseline Ophthalmology exam may occur at any time between the screening visit and the enrollment visit, including on the day of the screening visit or the enrollment visit. Prior baseline exam will be accepted if done within 45 days of enrollment.

⁴ Only if obtained as SOC. Not required specifically for study.

⁵ Screening CBC and CMP must be obtained within 2 months prior to enrollment. If not available or abnormal from previous SOC labs, CBC and CMP must be obtained prior to enrollment.

⁶ ANA results required prior to enrollment.

⁷ See Table 5 for specific instructions.

⁸ For females with childbearing potential and should be repeated at any time during study duration per standard of care by participant's provider.

⁹ Subjects who have not been screened for Hepatitis B as part of SOC will get one as part of screening or enrollment. Study drug can be dispensed prior to obtaining study results. Patient families will be instructed to not administer drug until a negative result is confirmed. If test results are positive, the subject will be discontinued from the study.

¹⁰ Enrollment may occur during screening visits or at a separate specific enrollment visit.

¹¹ Subjects who did not have a Quantiferon Gold or TB test as part of SOC will get one as part of screening or enrollment. Study drug cannot be administered in the absence of a negative test result.

¹² A 3- or 6-month supply of abatacept will be provided at the enrollment visit. Re-supply will occur at M3 if a 3-month supply was provided at enrollment.

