3.3 Clinical Trial Exclusion Criteria

The presence of any of the following will exclude a study participant from inclusion in the study:

1. Systemic JIA as defined by 2004 ILAR criteria¹
2. Sacroiliitis (clinical or radiographic)
3. Inflammatory bowel disease (IBD)
4. History of psoriasis or currently active psoriasis
5. History of uveitis or currently active uveitis
6. Prior treatment with systemic medication(s) for JIA (e.g. one or more of the following: DMARD or biologic medication)
7. Current or previous (within 30 days of enrollment) treatment with systemic glucocorticoids (A short course of oral prednisone [\leq 14 days] is allowed)
8. History of active or chronic liver disease
9. Chronic or acute renal disorder
10. AST (SGOT), ALT (SGPT) or BUN \geq 2 x ULN (upper limit of normal) or creatinine \geq 1.5 mg/dL or any other laboratory abnormality considered by the examining physician to be clinically significant within 2 months of the enrollment visit
11. Presence of any medical or psychological condition or laboratory result which would make the participant, in the opinion of the investigator, unsuitable for the study

12. Participation in another concurrent clinical interventional study within 30 days of enrollment
13. Known positive human immunodeficiency virus (HIV)
14. Received a live virus vaccine within 1 month of the baseline visit
15. Current or prior positive Purified Protein Derivative (PPD) test or Quantiferon Gold TB
16. Pregnant, breast feeding, or planned breast feeding during the study duration
17. Planned transfer to non-participating pediatric rheumatology center or adult rheumatologist in the next 12 months
18. Active malignancy of any type or history of malignancy
19. Chronic or active infection or any major episode of infection requiring hospitalization or treatment with intravenous (IV) antibiotics within 30 days or oral antibiotics within 14 days prior to screening
20. Primary language other than English or Spanish
21. Positive for Hepatitis B surface antigen or core antibody
22. <10 Kg in weight
23. If a potential subject has symptoms consistent with COVID-19 and/or known COVID-19 exposure at screening, it is recommended that the site follow CDC guidance regarding testing and quarantine requirements. The subject can be re-screened when there is no longer concern for active infection. A subject with a positive COVID -19 test may be re-screened.

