- **Patient Reported Outcomes Measurement Information System (PROMIS®) & other PRO Measures Appendix A:** PROMIS® fatigue, mobility, upper extremity function, pain interference, anxiety, depression, and global health measures will be administered via tablet or paper short-forms to the participant and/or guardian per CARRA Registry protocols. Other PROs collected are the Parent Global Assessment of overall wellbeing (11-point scale, 0 to 10 in increments of 1) and the Childhood Health Assessment Questionnaire (CHAQ). JAMAR, Covid Survey. Refer to Appendix for assessment details.

- **Serious Adverse Events (SAEs):** Occurrence of any serious adverse events from time of informed consent.
- **Events of Special Interest (ESIs):** Protocol-defined adverse events of special interest will be collected from time of informed consent. Refer to 7.5.
- **TB screen:** Participants can be screened by either Quantiferon Gold assay or PPD per the treating physician. If a Quantiferon Gold or PPD has been performed within the prior 6 months and is negative, it need not be repeated at screening, unless the participant has changed from low to high risk. Subjects may be enrolled before PPD or Quantiferon Gold assay TB results are reported. Subjects who did not have a Quantiferon Gold or PPD as part of SOC will get one as part of screening or enrollment. However, study drug can be dispensed prior to obtaining study results. Patient families will be instructed not to administer drug until a negative result is confirmed. If test results are positive, the subject will be discontinued from the study.
- **Urine pregnancy screen:** Menstruating females must have a negative urine pregnancy test at enrollment and for the duration of the trial. The test may be repeated at any time during study duration per standard of care by participant's provider.
- **Laboratory Assessments**
 - **ANA**
 - ANA results drawn at or after diagnosis of JIA may be used.
 - ANA results are required prior to enrollment.
 - **HLA-B27, RF, CCP:**
 - If these were obtained during initial evaluation for JIA, they do not need to be repeated.
 - Results are not required prior to enrollment and are not part of the study eligibility criteria.
 - **CBC/CMP :**
 - Screening CBC (hemoglobin, platelets and white blood cell count) and CMP (ASP/ALT/Creatinine) must be obtained within 2 months prior to enrollment. If not available or abnormal from previous SOC labs, CBC and CMP must be obtained prior to enrollment.

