 - Month 3/6: Only if obtained as SOC. Not required specifically for study.
 - **ESR/CRP:**
 - Results not needed prior to enrollment. Results will be captured at each study visit if obtained as part of SOC; however, not required as part of the Limit-JIA study
 - **Hepatitis B**

- All patients receiving abatacept should be screened clinically and undergo serologic testing if indicated for viral hepatitis prior to use as anti-rheumatic therapy may cause reactivation of hepatitis B.
- Subjects who have not been screened for Hepatitis B as part of SOC will get one as part of enrollment. Study drug can be dispensed prior to obtaining study results. Patient families will be instructed to not administer drug until a negative result is confirmed. If test results are positive, the subject will be discontinued from the study.

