6.1 Abatacept (Orencia) – Study Drug

Participants enrolled to receive SQ abatacept (Orencia) will receive training and study materials (3 month or 6 month drug supply) on the day of enrollment. The first dose should be administered at the site or at home with telehealth guidance from the investigator or other study staff once all test results have been verified. All study participants enrolled will be trained by the study staff on study drug administration. A resupply of IP will occur at the three-month visit if a 6-month supply was not provided at enrollment.

The 50 mg, 87.5 mg and 125 mg SQ doses that are approved for use in pediatric patients in the United States will be supplied by a US-based depot. The 125 mg SQ dose approved for use in Canada will be sourced from a Canadian vendor.

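### Pre-dose screening text conflicts: one Table 2 clause allows dosing without a TB result while four other statements withhold it, and only one of the two hepatitis B markers in exclusion 21 has a named test

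*Combined protocol and SAP*

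**What the plan says.** **TB.** The Quantiferon Gold/TB row of Table 2 (section 4.3.1) carries a parenthesis stating that "drug can be administered in the absence of test results". The same parenthesis goes on: "Patient families will be instructed to not administer drug until a" negative result has been confirmed (the sentence runs over a page break). Footnote 11, attached to that row, reads "Study drug cannot be administered in the absence of a negative test result". Section 4.3.2, under the TB screen, lets children be enrolled before the result is reported. It adds "However, study drug can be dispensed prior to obtaining study results" and then repeats the instruction that families must wait for a negative result. Section 6.1 places the first dose "once all test results have been verified".

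**Hepatitis B.** Exclusion 21 in section 3.3 reads "Positive for Hepatitis B surface antigen or core antibody". Table 2 has one hepatitis B row, labeled HBsAg and marked at the screening visit. Its footnote 9 says "Subjects who have not been screened for Hepatitis B as part of SOC will get one as part of screening or enrollment", with no dosing until a negative result. Section 4.3.2 says "All patients receiving abatacept should be screened clinically and undergo serologic testing if indicated for viral hepatitis prior to use", cites hepatitis B reactivation as the reason, and then repeats the footnote's rule for children not yet screened. The screening-visit list in section 4.6 includes hepatitis screening, qualified as being done where indicated. Section 4.7 requires review of the eligibility criteria before enrollment.

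**The concern.** These are the rules that sites apply before a child receives the first dose, and the schedule table is where staff are likely to look first. For TB, a row says drug may be given without a result while the footnote on that row says it may not. Both cannot be followed. The way drug is supplied makes clear wording more important: enrollment may precede the TB result, a 3- or 6-month supply is provided at the enrollment visit, and the first dose may be given at home under telehealth guidance. A family can therefore hold months of drug before the result exists, and the main remaining safeguards are the written instruction and staff verification of results.

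For hepatitis B the difficulty is a mismatch rather than a head-on contradiction. An exclusion criterion with two limbs is paired with a schedule that names a test for one. If the second limb is meant to operate, nothing in the visit lists tells a site to obtain the result it depends on. The protocol's own warning about reactivation shows that it treats hepatitis B status as a safety matter.

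**Working it through.** No arithmetic applies and the plan states no figure to reproduce. The check sets every statement on TB or hepatitis B screening and first-dose timing side by side.

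**TB: may drug be given before a negative result?**

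| Place | Reading |
|---|---|
| Table 2, TB row, first clause | Yes |
| Table 2, TB row, next sentence of the same cell | No; families wait for a negative result |
| Table 2, footnote 11 | No |
| Section 4.3.2, TB screen | No; dispensing is allowed, administration is not |
| Section 6.1 | No; the first dose follows verification of all results |

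One statement permits and four withhold. The clause that permits is complete in the text. The page break splits only the sentence after it, so the conflict is not an artifact of extraction. It bears only on children without an accepted negative test, because section 4.3.2 accepts a negative result from the prior 6 months unless the child has moved from low to high risk.

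**Hepatitis B: where is each marker named?**

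| Place | Surface antigen | Core antibody |
|---|---|---|
| Exclusion 21 (section 3.3) | Named | Named |
| Table 2 row | Named | Not named |
| Footnote 9 | Generic hepatitis B screen | Not named |
| Section 4.3.2 | Generic serology | Not named |
| Section 4.6 list | Generic hepatitis screening | Not named |
| Section 4.7 list | Not named | Not named |

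Core antibody has one mention in the supplied text, in the exclusion itself. Taking the possible results in turn:

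- Surface antigen positive, whatever the core antibody: the scheduled test finds the child.
- Both negative: exclusion 21 does not apply.
- Surface antigen negative, core antibody positive: exclusion 21 applies, but the child is found only if a core-antibody result already exists from standard care.

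The gap is therefore the third group without such a result. The eligibility review in section 4.7 and the verification in section 6.1 do not close it, because each can act only on results of tests that were done.

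**Who is tested for hepatitis B?** Footnote 9 and the second hepatitis B bullet of section 4.3.2 test everyone not already screened. The first bullet of section 4.3.2 and the list in section 4.6 make testing conditional on indication. These can be read together, but the text does not say how.

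**The case against.** The strongest reply on TB is that the error is corrected within its own cell. The next sentence withholds dosing, as do the footnote and two sections. Section 4.3.2 and footnote 9 use the verb for dispensing where the TB row uses the verb for administering, and follow it with nearly the same instruction to families, so the row looks like a one-word slip. Early dosing would require a site to disregard the rest of the cell, its footnote and a staff-guided first dose. This stands as an account of the practical risk, which is limited. It does not make the row consistent with its footnote.

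On hepatitis B, the reply is that the generic wording can be read as covering both markers: footnote 9 asks for a hepatitis B screen, section 4.3.2 speaks of serology, exclusion 21 says which markers exclude, and criteria are reviewed before enrollment. A careful site could read it that way. But footnote 9 hangs on the HBsAg row, so a site could equally take a negative surface antigen as the result that releases drug. A standard-care screen using surface antigen alone would also meet the footnote.

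The conditional wording is the weakest strand. In section 4.6 it may mean only that testing is needed if not already done, which agrees with footnote 9. It is a looseness to tidy, not a contradiction.

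It is also fair to say that no affected child can be counted and that no inferential quantity changes. Both are granted. They bear on scale, not on whether the text is consistent.

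**Conclusion.** The concern holds on both parts. The first clause of the TB row cannot stand with the rest of its cell, footnote 11, section 4.3.2 or section 6.1. The core-antibody limb of exclusion 21 has no named test in the schedule, its footnotes or the visit lists.

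The rules apply to up to 89 planned enrollees. The TB conflict matters only for a child without an accepted recent negative test, at a site that reads the clause apart from the statements around it. The hepatitis B gap changes eligibility only for a child who is core-antibody positive and surface-antigen negative with no core-antibody result from standard care. The documents give no prevalence for either situation, so no count is offered. Power, type I error and the primary endpoint are untouched.

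The conclusion rests on the supplied text being complete for these sections. It takes no position on which dosing or testing rule is clinically right. Because this is operative pre-dose safety text and easily corrected, it should be settled before sites rely on it.

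**What to change.** Reconcile the Table 2 TB row with footnote 11 and sections 4.3.2 and 6.1 so that one rule on administration before a result appears in every place. Reconcile exclusion 21 with the Table 2 hepatitis B row, footnote 9 and sections 4.3.2 and 4.6 so that the tests listed, and the children who receive them, match the criterion as the sponsor intends it. The clinical rule in each case is for the sponsor to decide.

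The cost is wording in two table rows, their footnotes and the matching sentences in sections 3.3, 4.3.2, 4.6 and 6.1, as needed. Whether any assay changes depends on how the sponsor reconciles exclusion 21 with the schedule. No statistical section needs to change.

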6.4 Study Drug Discontinuation Criteria

Study participants who permanently stop study drug in Limit-JIA should be encouraged to continue in the study. If for any reason a study participant must permanently stop study drug, every effort should be made by the Site Investigator/staff to keep the study participant in the Limit-JIA study to collect important safety and clinical data.

Withdrawal from the Limit-JIA study does not automatically withdraw the study participant from the CARRA Registry.

Study participant must be permanently discontinued from the study drug if the following occurs:

- Positive urine pregnancy test
- Non-compliance with study drug. Study participants' compliance with study treatment will be assessed throughout the study. Participants who miss more than one dose should be re-educated on the requirement for treatment compliance. Every effort will be made to keep participants in the study and to re-educate those who continue to miss doses. Participants who continue to be non-compliant after multiple visit assessments may be permanently discontinued from study drug at the discretion of the Site Investigator after consultation with the sponsor.

- Non-compliance with weekly diary. Study participants' must complete their weekly electronic or paper diary between study visits. Participants who are non-compliant after multiple visit assessments may be permanently discontinued from study drug at the discretion of the Site Investigator after consultation with the sponsor.
- Serious Infection
- Physician discretion
- Achievement of any of the primary outcomes as defined in the protocol (disease extension, uveitis and/or need for escalation of systemic therapies)
- SAE attributed to abatacept
- AE attributed to abatacept that at the discretion of the site PI warrants drug discontinuation.
- Conversion to positive PPD or Quantiferon Gold assay result that occurs during the study (if tested as standard of care)

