6.4.3 Discontinuation of Study Drug

Study participants may choose to stop taking study drug before the end of the study. A participant may also be asked to stop study drug at the Site Investigator's discretion. Participants who have permanently discontinued study drug are not required to withdraw from the study. Participants who have permanently discontinued study drug and have not withdrawn consent may continue in the study and complete all remaining protocol specified visits.

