6.4.5 Withdrawal from Study

There are no pre-determined protocol-specific study withdrawal criteria, however, study participants may choose to withdraw from the study at any time and withdraw their consent from further participation in the study. The Site Investigator must document the reason (if specified by the participant) for the withdrawal of consent. Participants who wish to withdraw from further participation in the study should be encouraged to return to the clinic as soon as possible to complete the M12 End of Study Visit. Every attempt should be made to have all evaluations and procedures as outlined in the Schedule of Events performed. (see Table 2 in Section 4.3.1)

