8.2.4 Other Secondary Outcomes

Other outcomes describing the clinical course of study participants will include

- Proportion of children achieving clinical inactive disease and/or remission
- Number of new joints with arthritis.
- Cumulative number of glucocorticoid joint injections.
- Serious adverse events.
- Juvenile arthritis disease activity (JADAS) scores.
- Elapsed time from enrollment to disease extension, uveitis or systemic medication use.
- Proportion of participants with disease extension (development of polyarthritis or uveitis).

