9.3 Major Secondary Analyses

Secondary analyses will be done for two study populations. Participants randomized in Part I or assigned to the abatacept arm in Part II will comprise the enrolled population [N approximately equal to 126 (37 Part I, 89 Part II)]. The overall study population [N approximately equal to 554] will include the enrolled population and 428 patients from the CARRA Registry whose disease extension results provided the control mean in Part II.

Secondary analyses for the enrolled population

Secondary analyses will generally be conducted as planned in Part I, although estimation of treatment effects or treatment by factor differences will be imprecise, since more than 80% of participants in the enrolled population are expected to receive abatacept.

Description of the time to disease extension will include cumulative incidence curves for the composite primary outcome and for the components disease extension, uveitis, and initiation of DMARDs or other biologic medication.

Descriptive analyses will summarize participant and caregiver reported outcomes (continuous outcomes of pain interference, fatigue, upper extremity function, mobility, anxiety, depression and global health PROMIS® modules, medication side effects (JAMAR), and the CHAQ). These outcomes will be measured at baseline and follow-up visits as shown in Table 5, and will be analyzed using a mixed model for repeated measures. Preliminary analyses will be performed to identify a parsimonious covariance structure among the repeated measures. The model will include as fixed effects treatment, time, treatment x time interaction, the baseline value of the outcome and the two stratification variables, the risk categories for polyarthritis and uveitis. Time will be treated as a categorical variable. The restricted maximum likelihood (REML) method of estimation and the Kenward-Roger degrees of freedom correction will be used. Contrasts will be constructed among the model parameters to test specific hypotheses. Overall treatment effect will be assessed by testing the null hypothesis of no treatment difference averaged over time. If the treatment x time interaction is significant at $\alpha=0.10$, additional descriptive tests may be done for treatment differences at specific time-points. Since more than 80% of participants in the enrolled population are expected to receive abatacept, there will be limited statistical power to determine treatment effects on these outcomes.

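### Table 2 footnote 1 lists polyarthritis, uveitis and escape as examples of leaving the study, while sections 6.4 to 6.4.5 keep the child in, so post-event data for secondary outcomes may go uncollected

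*Combined protocol and SAP*

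**What the plan says.** Two parts of the combined protocol and SAP deal with a child who reaches an endpoint before month 12.

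- **Section 4.3.1, Table 2, footnote 1.** The End of Study visit takes place at the end of follow-up or "if the participant discontinues the study for any reason, including development of polyarticular JIA or anterior uveitis, escape from treatment arm". The same list goes on to safety concerns and withdrawal of consent.
- **Section 6.4.** Among the reasons to stop study drug permanently is "Achievement of any of the primary outcomes as defined in the protocol (disease extension, uveitis and/or need for escalation of systemic therapies" (the parenthesis closes there). The same section says: "Study participants who permanently stop study drug in Limit-JIA should be encouraged to continue in the study". It asks sites to work to keep such children in so that safety and clinical data are collected.
- **Section 6.4.3.** "Participants who have permanently discontinued study drug are not required to withdraw from the study". They may go on to complete the remaining visits.
- **Section 6.4.5.** "There are no pre-determined protocol-specific study withdrawal criteria".

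Several secondary results draw on data after a first event. Section 8.2.4 lists "Proportion of participants with disease extension (development of polyarthritis or uveitis" (again with the parenthesis closing there), together with inactive disease, new joints, joint injections and JADAS. Section 9.3 plans "cumulative incidence curves for the composite primary outcome and for the components disease extension, uveitis, and initiation of DMARDs" or other biologics, and a repeated-measures model for the PROs. Section 9.1 analyses enrolled participants who were evaluated for the outcome in question. Section 9.2 limits the primary population to children with a known status at month 12.

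**The concern.** The footnote sits under the table that sites use to schedule visits, and it presents reaching an endpoint as a way of leaving the study. The sections on stopping drug say the opposite. A site working from the table could close out a child who starts systemic medication at month 4. Polyarthritis or uveitis at month 8 would then go unrecorded in the trial. So would later new joints, injections, PROs, JADAS and inactive-disease status.

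The children affected are not a random subset. They are selected by having met the primary outcome, so their missing data are tied to how their disease went. For the secondary proportion with polyarthritis or uveitis, starting medication would become an informative end of observation. For month-12 summaries, the children observed would be mainly those without events. Data that were not collected cannot be restored at analysis.

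**Working it through.** **1. The plan's own figures.** Section 9.4.2 assumes event rates of 15% on abatacept (80 evaluable) and 34.3% in 428 Registry controls, with one-sided alpha 0.025 and a Wald test from a logistic model. With x and y the event counts in the two groups, z = log odds ratio / √(1/x + 1/(80 − x) + 1/y + 1/(428 − y)). Exact enumeration of the two binomials gives power 0.958, against 0.956 in Table 7. All seven rows of Table 7 reproduce, with a largest gap of 0.011 at N = 50. Enrolment is 80 / 0.9 = 88.9, hence 89. The rates and sample size are therefore sound inputs, and the footnote conflict changes neither.

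**2. The passages side by side.**

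| Question | Footnote 1, Table 2 | Sections 6.4, 6.4.3, 6.4.5 |
|---|---|---|
| What does polyarthritis, uveitis or escape lead to? | An example of discontinuing the study | Permanent stop of study drug |
| What happens to later visits? | End of Study visit held early | Child encouraged to stay; may complete them |
| Are there criteria for leaving the study? | Implied by the examples | None set in advance |

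No passage says which text governs, or how data collected after an event enter the 12-month secondary analyses.

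**3. Children exposed.** Number = N × event rate.

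- 15%: 80 × 0.15 = 12.0; 89 × 0.15 = 13.4.
- 34.3% (no effect): 80 × 0.343 = 27.4; 89 × 0.343 = 30.5.

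These are upper bounds. A child whose event is first found at the month 12 visit loses nothing.

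**4. Outcomes exposed.**

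- Composite event and its timing: already recorded at the event.
- Polyarthritis or uveitis as a secondary proportion, and the component curves: exposed when medication comes first.
- New-joint and injection counts: cut short.
- PROs, CHAQ, JADAS and inactive disease: no true month-12 value.

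**5. Size within the abatacept group (illustration).** The documents give no inactive-disease rates. Assume 60% of event-free children and 0% to 40% of event children are inactive at month 12. True proportion = (1 − e) × 0.60 + e × q, where e is the event rate and q the rate in event children. Omitting event children always gives 60%.

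- e = 0.15: the true value is 51% (q = 0) to 57% (q = 0.4), so the result is 3 to 9 points too high.
- e = 0.343: the true value is 39% to 53%, so the result is 7 to 21 points too high.

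**6. Direction against the Registry (illustration, q = 0.20).** Assume all controls are followed.

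- Everyone followed: abatacept 0.85 × 0.60 + 0.15 × 0.20 = 54.0%; control 0.657 × 0.60 + 0.343 × 0.20 = 46.3%; difference 7.7 points.
- Abatacept event children left out: 60.0 − 46.3 = 13.7 points, too favourable to abatacept.
- Abatacept event children kept but scored not inactive from their event-time visit: 0.85 × 0.60 = 51.0%; 51.0 − 46.3 = 4.7 points, too unfavourable.

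The same early closure can therefore push the comparison either way, depending on a data-handling rule that the plan does not state.

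**The case against.** The strongest reply is that the footnote orders nothing. It is conditional: it says when to hold a visit if a child leaves. The operative text on staying in the study is explicit, and section 6.4.4 has the child return after stopping drug to decide whether to withdraw. This stands in part. The loss is a risk that depends on how sites read the table, and a reader who inferred that the protocol removes these children would go too far. But the footnote does name these events as examples of leaving, and no text overrides it.

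Second, the children are not wholly lost. The early End of Study visit itself collects joint count, PROMIS, CHAQ and JADAS, and earlier visits stay in the mixed model. Section 6.4 adds: "Withdrawal from the Limit-JIA study does not automatically withdraw the study participant from the CARRA Registry". Section 10.2 collects PROs under the Registry protocol, and section 10.3 allows supplementation from medical records. This also stands. It is not a full substitute, because section 9.3 expects evaluation timing and missing-data patterns to differ between the trial and the Registry.

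Third, a reader might infer a bias in favour of abatacept, since the footnote does not bind the 428 Registry controls. The documents do not support that. They give no figure for Registry follow-up after an event, children may improve once treatment is escalated, and step 6 shows the sign changing with the handling rule. Moreover, section 9.3 names time to extension and PROs for the overall population, and section 9.4 leaves that population's other analyses to a separate SAP. The inactive-disease comparison with the Registry is thus one that the plan does not yet specify.

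**Conclusion.** The conflict is real and should be reconciled. If sites act on footnote 1, up to about 12 of 80 abatacept children at the planned rate, or about 27 of 80 at the control rate, may have no trial data after their first event. Because the loss depends on outcome, it can bias the secondary results listed in step 4. Its direction is not established, and the percentage-point shifts in steps 5 and 6 rest on assumed inactive-disease rates.

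It would be wrong to infer that the primary result is undermined: the first composite event is recorded when it occurs, and power is unaffected. One sentence is still needed, because section 9.2 does not say that an event before month 12 counts as a known month-12 status.

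**What to change.** Reconcile footnote 1 with sections 6.4 to 6.4.5. The changes concern follow-up and data use only.

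- Remove polyarticular JIA, anterior uveitis and escape from treatment arm from the footnote's examples of study discontinuation.
- State that a child who reaches a primary outcome or stops study drug has an Interim Visit at that time and is asked to continue the scheduled visits and eye exams to month 12.
- Keep the early End of Study visit for children who actually leave, for example by withdrawing consent. Table 2 footnote 9 and the TB and hepatitis B entries in section 4.3.2 also discontinue a child from the study after a positive result. Those entries and section 6.4.5 need reconciling with each other.
- In section 9.2, state that an event before month 12 counts as disease status determined.
- In section 9.3, state that an event-time visit is not used as the month-12 value, and say how post-event data enter the secondary analyses.

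The cost is a text amendment, a note to sites and a few more visits for children with events. Those visits are already in the schedule.
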